#### **3.2.2.1 Study EMR100070-001**

Pharmacokinetics following the first 1-hour infusion and dose proportionality of avelumab have been characterized in 77 mainly Caucasian subjects treated in the dose escalation and expansion cohort of the Phase I Study EMR100070-001 by standard noncompartmental analysis based on

rich serum concentration-time data obtained over a complete dosing interval of 2 weeks (= tau). The exposure parameters maximum concentration ( $C_{max}$ ) and area under the concentration-time curve (AUC) after first dose generally increased in an approximately dose-proportional manner in the range from 3 to 20 mg/kg. The concentration at the end of dose interval ( $C_{min}$ ) increased proportionally with dose between 10 to 20 mg/kg, but more than proportionally for doses between 1 to 10 mg/kg. The total systemic clearance was low, 0.37 mL/h/kg  $\pm$  0.11 mL/h/kg at the 10 mg/kg dose (n = 40).

The terminal half-life ( $t_{1/2}$ ) increased with dose. However, the average values were 102 hours and 120 hours for 10 mg/kg and 20 mg/kg doses, respectively, with no significant difference between these 2 dose groups. Trough concentrations were obtained for the majority of subjects enrolled in the study. The mean  $\pm$  standard deviation trough concentration at the end of the first cycle for all cohorts receiving 80%-120% of the planned 10 mg/kg dose was 21  $\pm$  12  $\mu$ g/mL (n = 283). This median trough concentration increased during subsequent cycles to 25  $\pm$  16  $\mu$ g/mL (2nd cycle) (n = 269), 27  $\pm$  17  $\mu$ g/mL (3rd) (n = 202), 27  $\pm$  17  $\mu$ g/mL (4th) (n = 171), 28  $\pm$  19  $\mu$ g/mL (5th) (n = 145), 29  $\pm$  18  $\mu$ g/mL (6th) (n = 122), 34  $\pm$  18  $\mu$ g/mL (9th) (n = 81), and 36  $\pm$  18  $\mu$ g/mL (12th cycle) (n = 55).

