#### 3.3.1 Rationale for 10 mg/kg Once Weekly Dose-Escalation Cohort

Avelumab dosing regimen of 10 mg/kg once weekly for the first 12 weeks followed by once every 2 weeks starting at Week 13 would be evaluated with the following considerations:

- An exposure-efficacy response relationship was observed in second-line NSCLC subjects treated with 10 mg/kg once every 2 weeks. In 184 avelumab-treated subjects, unselected for PD-L1 expression, ORRs were 8.7%, 10.9%, 19.6%, and 17.4% for increasing quartiles of trough concentrations after first dose ( $C_{\text{troughfirst-dose}}$  Q1-4). Using  $\geq 1\%$ ,  $\geq 5\%$ ,  $\geq 50\%$ , and  $\geq 80\%$  PD-L1 staining cutoffs, subjects in the upper half of exposure ( $C_{\text{troughfirst-dose}}$  Q3-4 [n = 92]), had ORRs of 25% (n = 59), 26% (n = 39), 33% (n = 21), and 43% (n = 14),

respectively (data on file). The trends of longer progression-free survival (PFS) and OS for subjects in the higher exposure quartiles based on steady state trough concentration was also seen in the cohorts of urothelial cancer, gastric cancer, and others.

- Population PK analysis and simulation showed that a 10 mg/kg once every week regimen will increase the exposure, the median steady state trough concentration is predicted to increase from 22.9 µg/mL (range: 4.2-74.5 µg/mL) in the once every 2 weeks regimen to 83.3 µg/mL (range: 28.6-204 µg/mL) in the once weekly regimen (data on file), potentially enhancing efficacy as suggested by the exposure-efficacy analyses described above.
- In the above second-line NSCLC cohort, higher avelumab exposure was associated with a modest increase in immune-related AEs (irAEs). For all other AEs analyzed, AE incidence appeared to not increase with increasing exposure. And based on population PK modeling, median exposures are not expected to exceed those for previously administered regimens; the steady state maximum concentration is similar to that for 10 mg/kg once every 2 weeks regimen, while steady state AUC is similar to that for 20 mg/kg once every 2 weeks regimen (data on file).

In summary, the dosing regimen of 10 mg/kg once a week for 12 weeks followed by 10 mg/kg once every 2 weeks starting at Week 13 is supported by the exposure-efficacy relationship, time-to-response analyses, and an acceptable benefit-risk profile, as described above.

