## 7.5 Pharmacokinetics

Full PK blood samples will be collected from all subjects according to the following schedules as indicated in Table 1-3 and Table 1-4.

For subjects receiving avelumab once every 2 weeks:

[figure not shown]
- Day 1: within 2 hours prior to and at the end of the 1-hour infusion and at 0.5, 1, 2, 4, 6, and 12 hours after the end of the infusion.
- Day 2: 2 samples will be collected 24 and 36 hours after the end of the infusion.
- Day 3: a single sample will be collected 48 hours after the end of the infusion.
- Day 8: a single sample will be collected 168 hours after the end of the infusion.
- Days 15, 29, 43, 85, 127, and 169 (Week 25): samples will be collected within 2 hours prior to infusion (trough value) and immediately after the infusion is completed (peak value).
- Every 12 weeks beyond Week 25: a single sample will be collected within 2 hours prior to infusion (trough value).
- EOT Visit.
- 30-day Safety Follow-up Visit.

\*The time window for PK sampling time points are: +10 minutes for the end of infusion sample collection on Day 1;  $\pm 10$  minutes for 0.5 and 1 hour after the end of infusion;  $\pm 20$  minutes for 2, 4, and 6 hours after the end of infusion;  $\pm 2$  hours for 12, 24, 36, 48, and 168 hours after the end of infusion. The time window for PK sampling time points is applicable for all scheduled PK sample collection for all subjects.

For the 6 subjects receiving avelumab once a week:

- Within 2 hours prior to each infusion at Weeks 1, 2, 3, 5, and 7, at Weeks 13, 15, 19, and 25, and then at 12-week intervals while on treatment.
- At the end of infusion (within 15 minutes) at Weeks 1, 7, 13, and 25.
- EOT Visit.
- 30-day Safety Follow-up Visit.

CCI

The collection of blood samples with exact date and clock time of avelumab administrations (relative to the previous and next doses of avelumab) and sample collection will be recorded on the corresponding eCRF page. Whole blood sufficient to provide 1.5 mL of serum will be collected for all PK assessments. Postinfusion samples should be collected from a site other than the avelumab infusion site (ie, contralateral arm) on the days of infusion. If the infusion is interrupted, the reason for interruption will be documented on the eCRF.

Further instructions for PK sample collection and handling will be provided in a separate Laboratory Manual.

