## 8.5 Description of Statistical Analyses

### 8.5.1 General Considerations

All data recorded during the study will be presented in individual data listings for the Safety Analysis Set. Unless otherwise specified, all data will be evaluated as observed, and no imputation method for missing values will be used. All data will be presented in a descriptive manner.

Descriptive statistics will be used to summarize the study results, ie, statistics for continuous variables may include means, medians, ranges, and appropriate measures of variability. Qualitative variables will be summarized by counts and percentages. The uncertainty of estimates will be assessed by CIs. Unless otherwise specified, the calculation of proportions will be based on the sample size of the population of interest. Counts of missing observations will be included in the denominator and presented as a separate category if not otherwise specified in the SAP.

Full details of the planned analyses will be provided in the SAP.

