9.3.5 Handling of Missing Data

Unless otherwise specified (Section 11, 13, 14 and 15), missing data will not be imputed.

In all subject data listing imputed values will be presented. In all listings imputed information will be flagged. Partial dates, which are not to be imputed according to this IAP, will be presented in the format like “____YYYY”. In case imputation is defined, imputed date with flag (i.e., D for day, M for month) will be reported.

Missing statistics, e.g. when they cannot be calculated, should be presented as “NA”. For example, if n=1, the measure of variability (SD) cannot be computed and should be presented as “NA”.

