9.3.6 Presentation of PK Concentration Data

Individual PK concentrations will be reported with the same precision as the source data provided by the bioanalytical laboratory or clinical laboratory regardless of how many significant figures or decimal places the data carry. Actual elapsed sample collection times will be rounded to 2 decimal places for reporting purposes only, in by-subject listings.

Pharmacokinetic concentration data will be descriptively summarized using: number of non-missing observations (n), arithmetic mean (Mean), standard deviation (SD), coefficient of variation (CV%), minimum (Min), median (Median), and maximum (Max).

Descriptive statistics of PK concentration data will be calculated using values with the same precision as the source data, and rounded for reporting purposes only. The following conventions will be applied when reporting descriptive statistics of PK concentration data:

- Mean, Min, Median, Max: 3 significant digits
- SD: 4 significant digits
- CV%: 1 decimal place

Values below the lower limit of quantification (LLOQ) will be taken as zero in the calculation of descriptive statistics for avelumab serum concentrations.

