16.1 Pharmacokinetics

Serum concentrations and PK parameters will be listed by dose level, study day, and/or scheduled time point, as appropriate, and summarized using descriptive statistics as described in Section **Error! Reference source not found.**

Graphical displays of individual and mean (\pm SD for linear profiles only) serum concentration-time profiles will be presented on linear and semi-logarithmic scales by dose level up to 336 hours post-dose for the bi-weekly cohorts. Mean (\pm SD, linear profiles only) trough serum concentration-time profiles will be prepared for the once-weekly and bi-weekly cohorts. Individual serum concentration-time profiles will be presented on linear scale by study day for the once-weekly cohort.

For the PK analysis, pre-dose sample concentrations that are below the limit of quantification (BLQ) will be assigned a numerical value of zero for the calculation of AUC. On Day 1, any missing pre-dose value will also be assigned a numerical value of zero for the calculation of AUC. Any anomalous concentration values observed at pre-dose will be used as such in the PK analysis and identified in the CSR. All post-dose BLQ concentrations will be set to 'zero' in all cases.

Noncompartmental computation of PK parameters will be performed for the 3 mg/kg, 10 mg/kg, and 20 mg/kg once every 2 weeks dose escalation cohorts. Pharmacokinetic parameters will be evaluated and listed for all patients who provide sufficient concentration-time data. At least 3 valid, post-dose concentrations will be required in the PK profile to obtain any PK parameter estimate.

Individual PK parameters will be calculated using actual elapsed time from dose with a maximum of 14 significant digits in the time data (or using scheduled time if actual time is not available). The pre-dose sample will be considered as if it had been taken simultaneously with the administration of IMP. For any interim analyses, nominal time from dose will be used to calculate PK parameters.

Partial area $AUC_{0-\tau}$ should be calculated using the scheduled dosing interval, as defined in the CTP. The actual dosing interval calculated from CRF time data should not be used. The following rules apply when calculating the partial area $AUC_{0-\tau}$ within the observed time interval from T_1 to T_2 :

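### Multi-dose troughs are summarised only as visit means over subjects still on treatment, so accumulation cannot be told apart from a change in who remains

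*SAP*

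**What the plan says.** PK profiles are one of the two primary endpoints (protocol 8.3.1). SAP 16.1 derives AUC, Cmax, half-life and the related parameters from the Day 1 profile of the every-2-weeks cohorts only. Individual and mean concentration-time plots for those cohorts end at 336 hours. Beyond that, the visible plan lists concentrations, summarises them by time point, and states that mean "trough serum concentration-time profiles will be prepared for the once-weekly and bi-weekly cohorts". Individual profiles by study day are planned for the weekly cohort.

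SAP 9.3.6 summarises concentrations over non-missing observations, giving n, mean, SD, CV%, minimum, median and maximum. On missing data, SAP 9.3.5 says "Unless otherwise specified (Section 11, 13, 14 and 15), missing data will not be imputed", and the PK section is not among the exceptions. Protocol 8.5.1 likewise has data evaluated as observed. Troughs are pre-infusion samples; for the weekly cohort, protocol 7.5 schedules the late ones "and then at 12-week intervals while on treatment". Treatment runs until progression, clinical deterioration, unacceptable toxicity or another withdrawal criterion.

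The visible SAP 16.1 has no within-subject trough ratio, no profile for a fixed set of subjects and no model.

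**The concern.** Each visit mean answers what the trough is among those who remain. Accumulation asks a different question: how a subject's own trough changes on repeated dosing. The two agree only if leaving treatment is unrelated to trough.

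The protocol gives reason to doubt that. Section 3.3.1 reports response rates of 8.7%, 10.9%, 19.6% and 17.4% by rising quartile of first-dose trough. It also reports trends of longer PFS and OS for "subjects in the higher exposure quartiles based on steady state trough concentration was also seen in the cohorts of urothelial cancer" and other tumours. If low-trough subjects progress sooner, they leave sooner, and the later means rise with no change in anyone.

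Such means are readily read as a time trend. Of the global study, protocol 3.2.2.1 says "This median trough concentration increased during subsequent cycles to 25" µg/mL and then gives values up to 36 µg/mL, while n falls from 269 to 55. This trial would present the same kind of series from cohorts of 3 to 6 subjects, and it is meant to support comparison across studies for ethnic sensitivity (protocol 5.1.1.1 and 5.2.2).

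**Working it through.** **Inputs from the protocol.** First-cycle trough at 10 mg/kg: 21 ± 12 µg/mL, n = 283 (3.2.2.1). Later troughs: 25 (cycle 2, n = 269), 29 (cycle 6, n = 122), 36 (cycle 12, n = 55). Half-lives in Table 3-1: 85 to 127 h over all groups, 102 and 127 h at 10 mg/kg. Predicted median steady-state troughs: 22.9 µg/mL every 2 weeks and 83.3 µg/mL weekly (3.3.1).

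**Assumptions, not in the documents.** Mono-exponential decline; lognormal troughs; 43% retained; correlation of 0.2, 0.3 or 0.5 between log trough and time on treatment; for the simulation, 3 of 6 subjects retained and within-subject log noise SD 0.2.

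**1. Accumulation to expect every 2 weeks.** With r = 2^(−336/t½), the trough ratio of steady state to first dose is 1/(1 − r).

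| t½ (h) | r | 1/(1 − r) | cycle 2 to steady state, [1/(1 − r)]/(1 + r) |
|---|---|---|---|
| 85 | 0.065 | 1.07 | 1.00 |
| 102 | 0.102 | 1.11 | 1.01 |
| 127 | 0.160 | 1.19 | 1.03 |

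Expected accumulation is thus 7% to 19%. For weekly dosing (168 h in place of 336 h) the same formula gives 1.34 to 1.67.

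**2. Observed series in the global study.** 29/25 = 1.16 and 36/25 = 1.44, against 1.01 to 1.03 from step 1 at the 10 mg/kg half-lives. The reported figures do not show how much of the gap is attrition, a real change in clearance, or subjects who had not reached that cycle at data cutoff.

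**3. Size of a pure selection artefact.** σ = √ln(1 + (12/21)²) = 0.53. Retained fraction p = 122/283 = 0.43, used only as an illustrative value. With z the normal deviate cutting off the upper 43% (0.176), φ(z)/p = 0.393/0.43 = 0.913. With no true change, the retained subjects' central trough is inflated by exp(ρ × σ × 0.913) − 1:

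- ρ = 0.2: 10%
- ρ = 0.3: 16%
- ρ = 0.5: 27%

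**4. Cohorts of 6.** 200,000 simulated cohorts, 3 of 6 retained, true ratio 1.11, noise in both samples. The ratio of visit means has median 1.18, 1.22 and 1.30 at ρ = 0.2, 0.3 and 0.5. The paired geometric mean ratio stays at 1.11. At ρ = 0.2 the 5th to 95th percentile range is 0.74 to 1.74 for the ratio of means and 0.85 to 1.45 for the paired ratio. The widths are 1.00 and 0.60, so the paired range is about 40% narrower.

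**5. Different dropout model.** Here there is no true change, and the odds of dropout fall with exposure (odds ratio 1.5 to 3 per SD of log trough, assumed). The mean of those remaining is inflated 1.07- to 1.16-fold at 33% dropout and 1.10- to 1.25-fold at 50%. If the lowest 1, 2, 3 or 4 of 6 always left, the factors would be 1.11, 1.22–1.24, 1.36–1.39 and 1.54–1.59.

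**6. Regimen contrast.** 83.3/22.9 = 3.6. Even the worst case in step 5 is about 1.6.

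**The case against.** A reader might infer that the primary PK result as a whole is at risk. The documents do not support that: the noncompartmental parameters come from the first dosing interval and are unaffected by later dropout, and the Caucasian–Japanese comparison in Table 3-1 is also first-dose.

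A reader might also infer that attrition could produce a weekly versus every-2-weeks effect. It could distort the size of a 3.6-fold difference but not create it. Both regimens lose subjects, and no formal comparison is visible.

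Nor is upward bias certain. Protocol 3.3.1 describes trends in other studies, and its response rates are not monotone. It also reports a modest increase in immune-related events with exposure, so withdrawals for toxicity could remove high-trough subjects. Treatment beyond progression is allowed.

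The sizes are illustrative. The 43% is not a retention rate, because the global study was still running at data cutoff. The accumulation benchmark may be too low. From cycle 1 to cycle 2 the trough rose 25/21 = 1.19 with 95% of subjects still contributing (269/283), where superposition gives 1.10 to 1.16. The lognormal median of 21 ± 12 is 18.2, and 22.9/18.2 = 1.26. Protocol 5.2.3 itself warns of nonlinearity.

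There are partial safeguards: n and median in the summaries, full listings, individual profiles for the weekly cohort, and extra displays at the pharmacokineticist's discretion (protocol 8.5.2.2). Parts of both documents are redacted, so the absence of a paired summary can be stated only for the visible text.

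All of this stands and limits the reach of the point. It does not remove it: a discretionary display is not pre-specified, and no individual every-2-weeks plot beyond 336 hours is described.

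**Conclusion.** The point holds for the multi-dose trough part of the PK endpoint. As planned, a change in the mean trough profile cannot be separated from a change in who remains. For the every-2-weeks cohorts, the possible artefact (about 10% to 27% under the assumed correlations and 43% retained) is comparable to the 7% to 19% accumulation expected from Table 3-1 under mono-exponential decline. For the weekly cohort, where the same formula gives 34% to 67% accumulation, it matters less. The direction and size in this trial are unknown. Nor does the rise from 25 to 36 µg/mL in the global study show attrition at work; it shows only that such a series is ambiguous. This is a cheap improvement to the plan, not a flaw that undermines the primary analysis.

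**What to change.** In SAP 16.1:

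- Add the within-subject ratio of each visit trough to the subject's own first trough: Day 15 for the every-2-weeks cohorts, Day 8 for the weekly cohort. Report n, the geometric mean ratio and the individual values, with a 95% CI where n allows (three subjects leave 2 degrees of freedom).
- Report by cohort and do not pool over doses, since protocol 3.2.2.1 reports that half-life rises with dose and that Cmin is more than proportional up to 10 mg/kg.
- In the weekly cohort, keep the ratios up to Week 13 apart from later ones. From Week 15 the trough follows a two-week interval.
- Add individual trough-versus-visit lines for the every-2-weeks cohorts, and print n at each visit on the mean trough profile.
- State that any accumulation statement is read from the within-subject ratios and that visit means are descriptive.

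The cost is a few lines of text, one table and one figure, from samples already scheduled. The downside is that the ratios use fewer subjects than the early visit means and describe only those with a later sample. They do not estimate the contrast between regimens.

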ADA: antidrug antibody; AE: adverse event; CR: complete response; CT: computed tomography; D: Day; DLT: dose-limiting toxicity; ECG: electrocardiogram; ECOG PS: Eastern Cooperative Oncology Group performance status; EOT: End-of-Treatment; hCG: human chorionic gonadotropin; HIV: Human immunodeficiency virus; ICF: Informed consent form; IMP: investigational medicinal product; MRI: magnetic resonance imaging; PD: progressive disease; CCI: [redacted] PK: pharmacokinetics; PR: partial response; RECIST: response evaluation criteria in solid tumors; SAE: serious adverse event; T4: thyroxine; TSH: thyroid-stimulating hormone; V: Visit; W: Week.

1. A time window of up to 3 days before or 1 day after the scheduled visit day (- 3/+ 1 days) is permitted for all study procedures (except for PK sampling visits on Day 2 and 3, see [Table 1-3](#)). The calculation of the dose of avelumab will be based on the weight of the subject determined within 72 hours prior to the day of drug administration.
2. All subjects will have an EOT Visit within 7 days after the decision to discontinue avelumab. In addition, subjects will be followed every 12 weeks ( $\pm 7$  days) for survival (including assessment of any further anticancer therapy).

CCI

[figure not shown]
4. If another anticancer therapy is administered before the end of this 7-day period, the EOT Visit should be conducted prior to the start of this new therapy, if possible. The EOT Visit may be performed on the day of the decision to discontinue avelumab.

CCI

7. Medical history should include history of cancer, previous and ongoing medications, previous surgeries, radiotherapies, baseline medical conditions, smoking and alcohol history, and family cancer history.
8. A full physical examination will be conducted at Clinical Screening, at the EOT Visit and at the 30-day Safety Follow-up Visit. During the Treatment Phase, the physical examination will be symptom-directed.
9. If the Clinical Screening ECOG PS was performed within 3 days prior to Day 1, it does not have to be repeated at Visit 1/Cycle 1 Day 1.
10. Enrolment will be done after confirmation that the subject meets all screening inclusion criteria ([Section 5.3.1](#)) without matching any exclusion criterion ([Section 5.3.2](#)).

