ADA: antidrug antibody; AE: adverse event; CR: complete response; CT: computed tomography; D: Day; DLT: dose-limiting toxicity; ECG: electrocardiogram; ECOG PS: Eastern Cooperative Oncology Group performance status; EOT: End-of-Treatment; hCG: human chorionic gonadotropin; HIV: Human immunodeficiency virus; ICF: Informed consent form; IMP: investigational medicinal product; MRI: magnetic resonance imaging; PD: progressive disease; CCI [REDACTED] PK: pharmacokinetics; PR: partial response; RECIST: response evaluation criteria in solid tumors; SAE: serious adverse event; T4: thyroxine; TSH: thyroid-stimulating hormone; V: Visit; W: Week.

[figure not shown]
1. A time window of 1 day before or 1 day after the scheduled visit day (- 1/+ 1 days) is permitted for all study procedures while subjects receiving avelumab once weekly (12 consecutive weeks). A time window of up to 3 days before or 1 day after the scheduled visit day (- 3/+ 1 days) is permitted for all study procedures while subjects receiving avelumab once every 2 weeks (Week 13 and thereafter). The calculation of the dose of avelumab will be based on the weight of subject determined within 72 hours prior to the day of drug administration.
2. Columns of EOT Visit, Safety Follow-up, and the Long-term Follow-up Visits are omitted due to layout readability. The procedures at EOT Visit, Safety Follow-up, and the Long-term Follow-up are identical to the procedures planned for subjects receiving avelumab once every 2 weeks (as shown in Table 1-1).

CCI [REDACTED]

4. Medical history should include history of cancer, previous and ongoing medications, previous surgeries, radiotherapies, baseline medical conditions, smoking and alcohol history, and family cancer history.
5. A full physical examination will be conducted at Clinical Screening, at the EOT Visit and at the 30-day Safety Follow-up Visit. During the Treatment Phase, the physical examination will be symptom-directed.
6. If the Clinical Screening ECOG PS was performed within 3 days prior to Day 1, it does not have to be repeated at Visit 1/Cycle 1 Day 1.
7. Enrolment will be done after confirmation that the subject meets all screening inclusion criteria (Section 5.3.1) without matching any exclusion criterion (Section 5.3.2).

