### 4.1 Primary Objectives

- To evaluate the MTD of avelumab monotherapy in Chinese subjects.
- To characterize the PK of avelumab in Chinese subjects.

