### 5.1.3.1 Adverse Drug Reactions Requiring Treatment Discontinuation or Modifications

The following adverse drug reactions (ADRs) require permanent discontinuation or treatment modification of avelumab treatment:

- Any Grade 4 ADRs: permanently discontinue avelumab except for laboratory values out of normal range that do not have any clinical correlation.
- Any Grade 3 ADRs:
  - Withhold avelumab except for laboratory values out of normal range that do not have any clinical correlate.
  - Permanently discontinue avelumab if toxicity does not resolve to Grade  $\leq 1$  or baseline within 12 weeks of last administration or if the same Grade 3 toxicity recurs (consider consult with the medical monitor before permanently discontinuing the treatment).
- Infusion should not be given if ECOG performance status is  $\geq 3$  on the day of study treatment administration. Treatment should be discontinued if ECOG performance status has not improved to  $\leq 2$  by the next scheduled treatment administration.
- Any Grade 2 ADRs should be managed as follows:
  - Infusion should not be given in case of ongoing Grade 2 ADR on the day of study treatment administration.
  - Treatment can be resumed according to original schedule\* once ADR resolved to Grade  $\leq 1$ . Up to 2 subsequent study drug doses may be omitted. If more than 2 doses are skipped, treatment may be resumed after consultation with the Medical Monitor.

\*Original schedule is defined as “the dosing schedule calculated according to first dose”.

If dosing is delayed more than 4 weeks, treatment may be resumed after consultation with the study Medical Monitor. Any delay in dosing in excess of 12 weeks is not permitted.

Infusion-related reactions and irAEs should be handled according to the guidelines provided in Sections 6.5.5.1 and 6.5.5.2, respectively.

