### 7.5.1 Pharmacokinetic Parameters

The following PK parameters will be calculated using noncompartmental analysis:

- $AUC_{0-t}$ : area under the concentration-time curve from time zero to time t (calculated by linear trapezoidal summation).
- $AUC_{0-\tau}$ : area under the concentration-time curve from time zero to tau, the respective dosing interval, ie, 1-week or 2-week (calculated by linear trapezoidal summation).
- $AUC_{0-\infty}$ : area under the concentration-time curve from time zero to infinity (calculated by the linear trapezoidal summation and extrapolated to infinity using  $C_{last}/\lambda_z$ ).
- $\lambda_z$ : terminal elimination rate constant. The value of  $\lambda_z$  is determined from the slope of the regression line of log (concentration) versus time.
- $C_{max}$ : maximum serum concentration.
- $C_{trough}$ : serum concentration observed immediately before next dosing.
- $C_{last}$ : last quantifiable concentration.
- $t_{max}$ : time to maximum concentration.
- $t_{1/2}$ : elimination half-life determined as  $0.693/\lambda_z$ .

CCI

CCI

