C_{last}	Last quantifiable serum concentration observed, obtained directly from the concentration versus time curve. Units: μ g/mL.
C_{trough}	The concentration observed immediately before next dosing. Units: μ g/mL.

t_{\max}	Time to reach maximum serum concentration, obtained directly from the concentration versus time curve. Units: h.
$t_{1/2}$	Terminal elimination half-life, determined as $\ln(2)/\lambda_z$. Units: h.
AUC_{0-t}/dose	Dose-normalized AUC_{0-t} . Actual mg/kg dose administered will be used in the calculation of this parameter. Units: $(h*\mu\text{g/mL})/(\text{mg/kg})$.
$AUC_{0-\tau}/\text{dose}$	Dose-normalized $AUC_{0-\tau}$. Actual mg/kg dose administered will be used in the calculation of this parameter. Units: $(h*\mu\text{g/mL})/(\text{mg/kg})$.
C_{\max}/dose	Dose-normalized C_{\max} . Actual mg/kg dose administered will be used in the calculation of this parameter. Units: $(\mu\text{g/mL})/(\text{mg/kg})$.

The following PK parameters will be calculated for diagnostic purposes and listed, but will not be summarized:

- The time interval (h) of the log-linear regression ($\lambda_{z\text{ low}}, \lambda_{z\text{ upp}}$) to determine λ_z ($t_{1/2}$, Interval).
- Number of data points (N_λ) included in the log-linear regression analysis to determine λ_z .
- Goodness of fit statistic (Rsq) for calculation of λ_z .

The regression analysis should contain data from at least 3 different time points in the terminal phase consistent with the assessment of a straight line on the log-transformed scale. Phoenix WinNonlin best-fit methodology will be used as standard. The last quantifiable concentration should always be included in the regression analysis, while the concentration at t_{\max} and any concentrations <LLOQ which occur after the last quantifiable data point should not be used.

The coefficient of correlation (Rsq) should be ≥ 0.800 and the observation period over which the regression line is estimated should be at least twofold the resulting $t_{1/2}$ itself. If %AUC_{extra} is greater than 20%, the rate constants and all derived parameters (e.g., $t_{1/2}$, $AUC_{0-\infty}$) will be included in the parameter outputs and descriptive statistics but will be flagged and discussed appropriately. Any flags should be included in the study specific SDTM.

Scatter-plots of individual patient data and GeoMean values of C_{\max}/dose , $AUC_{0-\tau}/\text{dose}$, and AUC_{0-t}/dose versus dose will be prepared.

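### In the every-2-week cohorts, Ctrough is taken as observed although the next infusion may fall 3 days early or 1 day late, so permitted timing alone can raise a Day 15 trough by up to 1.48- to 1.80-fold.

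*SAP*

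**What the plan says.** Protocol 4.1 makes it a primary objective "To characterize the PK of avelumab in Chinese subjects". Protocol 7.5.1 lists Ctrough among the parameters, as the "serum concentration observed immediately before next dosing", and SAP 16.1 has the same definition: "The concentration observed immediately before next dosing". SAP 16.1 calculates it as a parameter only for the Day 1 profile of the bi-weekly cohorts. All other troughs enter as concentrations, and mean "trough serum concentration-time profiles will be prepared for the once-weekly and bi-weekly cohorts".

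Protocol 7.5 and Table 1-3 tie the predose sample to the infusion, within 2 hours before it. Table 1-1, footnote 1, lets the visit move: a window of "up to 3 days before or 1 day after the scheduled visit day (- 3/+ 1 days) is permitted for all study procedures", with only the Day 2 and Day 3 PK visits exempt. For weekly dosing, Table 1-2, footnote 1, states: "A time window of 1 day before or 1 day after the scheduled visit day (- 1/+ 1 days) is permitted for all study procedures". The PK sampling windows in Protocol 7.5 cover end of infusion and 0.5 to 168 h afterwards. None covers the time from the previous dose to a trough.

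For AUC0-tau, SAP 16.1 says that it "should be calculated using the scheduled dosing interval, as defined in the CTP". Protocol 5.1.3 and 5.1.3.1 allow doses to be skipped. SAP 16.1 uses anomalous predose values as they stand and identifies them in the study report.

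**The concern.** The SAP recognises for AUC0-tau that the actual dosing interval varies and removes that variation. It does not do so for Ctrough, which is the more sensitive to timing because it is a single point on the declining curve. A Day 15 trough may be a 264 h or a 360 h concentration and is summarised as if all were 336 h. The window is lopsided, with more room early than late, so the error leans towards high values and need not average out. After a skipped dose the predose sample is not a trough of the planned regimen at all.

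Troughs are part of the protocol's argument for the 10 mg/kg dose (3.2.3) and for the weekly regimen (3.3.1), and Cmin is in Table 3-1, which sets out earlier-study PK. Protocol 5.2.2 intends PK to be compared across studies, including for ethnic sensitivity. With 3 to 6 subjects per cohort, one or two early visits can move a cohort's trough summary.

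**Working it through.** The documents give no timing-sensitivity figure to reproduce, so the size is derived.

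**Inputs.** Mean half-lives in Protocol Table 3-1: 85, 102 and 120 h (global study) and 92, 127 and 115 h (Japanese study). Windows: -3/+1 days (every 2 weeks) and -1/+1 days (weekly). Applying these half-lives to Chinese subjects, and mono-exponential decay near the trough, are assumptions.

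**Plausibility of the model.** With one-compartment linear kinetics, the weekly to 2-weekly steady-state trough ratio is 1 + 2^(168/t½). Protocol 3.3.1 predicts 83.3/22.9 = 3.64; the formula gives 3.64 at 120 h, 4.13 at 102 h and 3.50 at 127 h.

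**One visit moved.** Fold change = 2^(hours early / t½).

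| t½ (h) | 2-weekly, 72 h early | 2-weekly, 24 h late | 2-weekly, edge to edge (96 h) | Weekly, 24 h early | Weekly, edge to edge (48 h) |
|---|---|---|---|---|---|
| 85 | 1.80 | 0.82 | 2.19 | 1.22 | 1.48 |
| 102 | 1.63 | 0.85 | 1.92 | 1.18 | 1.39 |
| 120 | 1.52 | 0.87 | 1.74 | 1.15 | 1.32 |
| 127 | 1.48 | 0.88 | 1.69 | 1.14 | 1.30 |

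**Average effect under an assumed spread.** If 2-weekly visits were uniform over days -3, -2, -1, 0 and +1, the mean shift is 1 day (24 h) early. The geometric mean then rises by 2^(24/t½) - 1, which is 14% at 127 h and 22% at 85 h. The SD of those offsets is √2 days = 33.9 h, so the added log-scale SD is 33.9 × ln 2 / t½, or 0.19 to 0.28. For scale, Table 3-1 Cmin at 10 mg/kg is 22 (SD 12) µg/mL, a log SD of √ln(1 + (12/22)²) = 0.51, and a standard error of 0.51/√6 = 0.21 with 6 subjects. The systematic shift is ln 1.14 to ln 1.22, or 0.13 to 0.20.

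**Skipped dose.** Let x = 2^(-336/102) = 0.102. The intended Day 29 trough, relative to one dose, is x + x² = 0.112. If Day 15 is skipped, the Day 29 predose sample is x² = 0.0104. The ratio is x/(1 + x) = 0.09, about one tenth.

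**Choice of interpolation.** For a Day 16 sample (360 h) and the 168 h sample at t½ 102 h, the relative concentrations are 0.0866 and 0.3193. Linear interpolation at 336 h gives 0.3193 - (168/192) × (0.3193 - 0.0866) = 0.1157, against a model value of 0.1019: about 13% too high. That is nearly the 15% timing error being corrected, so interpolation has to be on the log scale.

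**The case against.** The strongest reply is that little rests on Ctrough and that its timing can already be traced. SAP 16.1 assesses dose proportionality on AUC0-tau and Cmax only, and its dose-normalised plots use AUC and Cmax. No readable analysis tests Ctrough between doses, regimens or studies. Exact dosing and sampling times are recorded (Protocol 7.5). Actual elapsed times appear in by-subject listings (SAP 9.3.6), and days since the previous administration in the dosing listing (SAP 13.2). Under the uniform assumption the timing SD is well below the between-subject SD, and the mean shift is within one standard error at 6 subjects. All of this stands, and it limits the weight of the point. It does not supply a rule: a listing leaves the trough summaries and plots unchanged. Nor would the dose-delay table in SAP 13.2 show the problem, since it has no category for early doses and counts Day 17 as no delay.

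A reader might infer more than the documents support:

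- **That the 2-weekly fold changes apply to the weekly cohort.** One weekly visit moved gives at most 1.22-fold against nominal. Weekly troughs are not calculated as a parameter and enter only as concentrations and mean profiles.
- **That later 2-weekly troughs routinely vary 2.6- to 4.5-fold.** That needs two consecutive infusions at opposite window limits (intervals of 10 and 18 days). Anchoring to Day 1 is a fair reading of Table 1-1, but the phrase "the dosing schedule calculated according to first dose" in Protocol 5.1.3.1 defines the schedule only for resuming after a Grade 2 reaction.
- **That the rationale for 10 mg/kg is in doubt.** Troughs of 12.69 to 26.87 µg/mL (Protocol 3.2.3) lie far above the 1 µg/mL occupancy plateau, so a shift of this size leaves that inference alone.
- **That the ethnic comparison is biased.** This depends on how Cmin was timed in the two earlier studies, which the documents do not state.

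It would also be wrong simply to exclude off-interval samples. Under uniform visits, a 336 ± 24 h limit drops two of five permitted days, 40% of compliant Day 15 troughs, leaving about 3.6 of 6.

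**Conclusion.** The gap is real and worth closing, but it is confined to trough reporting. In the every-2-week cohorts a fully compliant Day 15 Ctrough can be 1.48- to 1.80-fold high, with a 1.69- to 2.19-fold spread between window edges. Those are bounds, not expected effects; an even spread of visits would raise the geometric mean by about 14% to 22%. Actual visit timing is unknown. The skipped-dose case is rarer but larger, with a Day 29 value near one tenth of the intended trough at 102 h. The weekly cohort is only mildly exposed.

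The figures rest on mono-exponential decay and on half-lives from the two earlier studies. The statement that no rule exists is limited to readable text, since redacted blocks follow the PK sections of the protocol. The primary PK objective is not undermined, because AUC0-tau and Cmax are not affected in this way.

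**What to change.** Amend SAP 16.1 and 9.3.6; no visit or dosing change is involved.

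1. Keep the observed Ctrough summary. Beside it, report for the Day 1 profile each subject's concentration at 336 h: extrapolated with the subject's lambda-z when the predose sample is earlier than 336 h, and interpolated log-linearly when it is later. State the interpolation rule explicitly, because SAP 16.1 interpolates linearly inside the sampled range and uses lambda-z only beyond the last measurable concentration. Where extrapolation is needed and lambda-z cannot be estimated, report no value, as the SAP already does for the partial area.
2. Leave predose samples that follow a skipped dose out of the Ctrough summaries and mean trough plots. List and flag them.
3. Flag other predose samples off the nominal interval, using a tolerance stated in the SAP, and show the actual elapsed time. Add a sensitivity summary without them, and keep protocol-compliant samples in the main summary.

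The cost is a small programming step on data already collected, one extra reported parameter, and a slightly smaller n at visits after a skipped dose.
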